2.3.3 Study duration per subject

For each subject, the study will last a maximum of up to 77 weeks, as follows:

- Screening Period: 2 to 5 weeks
- Double-blind, active-controlled Initial Treatment Period: 16 weeks
- Maintenance Treatment Period: 40 weeks
- Safety Follow-Up Period: a SFU Visit is planned 20 weeks after the last dose of IMP (for subjects not enrolling in the open-label study)

After the 40-week Maintenance Treatment Period, subjects will be allowed to enroll in an open-label study, in which case subjects will undergo the Week 56 study assessments before receiving their first open-label IMP dose. The SFU Visit will not be required for subjects who enroll in the open-label study.

The end of the study is defined as the date of the last visit of the last subject in the study.

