2.3.4 Planned number of subjects and site(s)

Approximately 600 subjects will be screened in order to have 450 subjects randomized in the study. There will be approximately 150 subjects per treatment arm. The planned number of study sites is approximately 100. Every eligible subject who signs an ICF will be expected to be randomized.

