3.6 Treatment assignment and treatment groups

It is expected that subjects receive treatment as randomized and hence safety analyses will be based on the SS, as randomized. However, if after unblinding it is determined that subjects randomized to a treatment arm had never received such treatment, then for safety analyses, these subjects will be reallocated to the appropriate received treatment groups, unless otherwise specified.

Efficacy analyses should be performed according to randomized treatment and not actual treatment received.

Summaries based on SS or RS will be provided by “BKZ 320mg Q4W”, “BKZ 320mg Q4W/Q8W”, “BKZ Total” and “ADA” treatment groups. The ADA group will only be presented from Baseline to Week 24 in the by-visit summaries.

Summaries based on BKZ Week 24 set will be provided by “BKZ 320mg Q4W”, “BKZ 320mg Q4W/Q8W” and “ADA/BKZ 320mg Q4W” treatment groups for disposition, baseline assessments and efficacy. The ADA/BKZ 320mg Q4W group will be presented from Week 28 to Week 56 in the by-visit summaries for the PASI scores and the DLQI only.

For safety, summaries on the BKZ set will be provided by “BKZ 320mg Q4W”, “BKZ 320mg Q8W” and “BKZ Total”. BKZ Q4W will include data from subjects in the BKZ Q4W/Q8W arm (up to Week 16) and the ADA/BKZ Q4W arm (after Week 24).

Safety summaries on the BKZ Week 24 set will be provided for subjects switching from Adalimumab to Bimekizumab.

Summaries based on the Maintenance set will be provided by “BZK 320mg Q4W”, “BKZ 320mg Q4W/Q8W” and “BKZ Total”.

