10.1.3 Exposure during the initial and maintenance period for BKZ Set

Definitions for study medication duration (days) and time at risk (days) through initial and maintenance treatment period are provided as follows:

For subjects randomized to BKZ Q4W/Q4W:

Study medication duration (days)

- Date of last dose of bimekizumab – date of first dose + 28 days

Note: If date of last dose of bimekizumab+ 28 days extends to a date beyond the final visit date (including PEOT, but not including SFU), then this calculation reverts to:

- Final visit date (including PEOT, but not including SFU) – date of first dose + 1.

Note: For subjects who die, if date of last dose of bimekizumab+ 28 days extends to a date beyond the date of death, then this calculation reverts to:

- Date of death – date of first dose + 1.

Time at risk (days):

- For subjects who continue into an open-label study (and, therefore, do not have the SFU visit in the feeder study): Final visit date – date of first dose + 1.
- For subjects who die prior to the final visit: Date of death – date of first dose + 1.
- For all other subjects, use the minimum of the following:
 - Date of last dose – date of first dose + 140 days.
 - Date of last clinical contact – date of first dose + 1.

Note: This group could include subjects who discontinue early, subjects who complete the Maintenance Period as scheduled but choose not to continue into an open-label study, or subjects who are ongoing in the SFU period at the time of the data snapshot.

For subjects randomized to BKZ Q4W/Q8W:

Study medication duration (days)

- Initial Treatment Period (attributed to BKZ Q4W)
 - Date of last dose of bimekizumab in the Initial Treatment Period – date of first dose in the Initial Treatment Period + 28 days

Note: If date of last dose of bimekizumab in the Initial Treatment Period + 28 days extends to a date beyond the date of the first dose in the Maintenance Treatment Period, then this calculation reverts to:

- Date of first dose in the Maintenance Treatment Period – date of first dose in the Initial Treatment Period + 1.

Note: For subjects who die during the Initial Period, if date of last dose of bimekizumab in the Initial Treatment Period + 28 days extends to a date beyond the date of death, then this calculation reverts to:

- Date of death – date of first dose in the Initial Treatment Period + 1.

- Maintenance Treatment Period (attributed to BKZ Q8W)

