10.2 Adverse events

An AE is any untoward medical occurrence in a subject or clinical investigation subject administered a pharmaceutical product that does not necessarily have a causal relationship with this treatment. An AE can therefore be any unfavorable and unintended sign (including an abnormal laboratory finding), symptom, or disease temporally associated with the use of a medicinal (investigational) product, whether or not related to the medicinal (investigational) product.

Adverse events will be coded according to the Medical Dictionary for Regulatory Activities (MedDRA version 19.0). For subjects who switch treatment during the study i.e. those randomized to BKZ Q4W/Q8W or ADA/BKZ, any adverse events that occur after initiation of the new treatment are attributable to the new treatment. If an adverse event occurs on the date of a treatment switch, the event is attributed to the original treatment. The only exception to this is if the AE fulfills the criteria for an anaphylactic reaction as defined in the bimekizumab safety topics of interest document. Specifically, this includes the following:

- Events that fulfill the anaphylaxis criteria for acute events (refer to Appendix A in section 12)
- Events with a reported term containing the term “hypersensitivity (SMQ)”
- Events with an HLT of “Administration site reactions NEC”
- Events with an HLT of “Injection site reactions”

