10.2.2 AE summaries

The following summaries will be provided in five different ways: through Week 24 for the SS, through initial and maintenance treatment period for the BKZ Set, through initial treatment period for the SS, through the maintenance period for the MS (excluding patients randomized to ADA) and from Week 24 to Week 56 for the BKZ Week 24 Set for patients randomized to ADA switching to BKZ (to examine the events occurring within 70 days and >70 days of the treatment switch).

- Incidence of TEAEs – Overview
- Incidence of TEAEs per 100 subject years by SOC, HLT, and PT
- Incidence of Serious TEAEs per 100 subject years by SOC, HLT, and PT

The following summary will be provided in four different ways: through Week 24 for the SS, through initial and maintenance treatment period for the BKZ Set, through initial treatment period for the SS and through the maintenance period for the MS (excluding patients randomized to ADA).

- Incidence of TEAEs Leading to Discontinuation per 100 subject years by SOC, HLT, and PT

The following summaries will be provided in two different ways: through Week 24 for the SS, and through initial and maintenance treatment period for the BKZ Set:

- Incidence of TEAEs Leading to Death by SOC, HLT, and PT
- Incidence of TEAEs by Maximum Relationship by SOC, HLT, and PT
- Incidence of Serious TEAEs by Relationship SOC, HLT, and PT – Note: For EudraCT reporting purposes
- Incidence of Related Serious TEAEs by SOC, HLT, and PT
- Incidence of TEAEs Leading to Death by Relationship by SOC, HLT, and PT – Note: For EudraCT reporting purposes
- Incidence of TEAEs by Maximum Severity, SOC, HLT, and PT
- Incidence of TEAEs by decreasing frequency of PT
- Incidence of TEAEs Above Reporting Threshold of 5% by SOC and PT
- Incidence of Non-Serious TEAEs by SOC, HLT, and PT
- Incidence of Non-Serious TEAEs by Relationship SOC, HLT, and PT
- Incidence of Non-Serious TEAEs Above Reporting Threshold of 5% by SOC and PT
- Incidence of Non-Serious TEAEs Above Reporting Threshold of 5% by Relationship SOC and PT
- Incidence of Related TEAEs by SOC, HLT, and PT
- Incidence of Related TEAEs Above Reporting Threshold of 5% by SOC and PT

The following summary will be provided through Week 24 for the SS:

- Incidence of TEAEs Above Reporting Threshold of 5% with Risk Differences by SOC and PT
- Incidence of Serious TEAEs and Risk Differences by SOC and PT

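### In BKZ Set AE tables all early bimekizumab time sits in the Q4W column, and the safety-topic, severity and relationship tables have no stated like-for-like version

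*SAP*

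**What the plan says.** SAP 3.6 gives three columns for safety summaries on the BKZ Set: Q4W, Q8W and Total. Of the first it says "BKZ Q4W will include data from subjects in the BKZ Q4W/Q8W arm (up to Week 16) and the ADA/BKZ Q4W arm (after Week 24".

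SAP 10.1.3 splits the exposure of the Q4W/Q8W arm in the same way: "Initial Treatment Period (attributed to BKZ Q4W" and "Maintenance Treatment Period (attributed to BKZ Q8W". SAP 10.2 does so for events in subjects who switch: "any adverse events that occur after initiation of the new treatment are attributable to the new treatment". The columns follow the regimen at the time of the event, not the randomised arm, and a Q4W/Q8W subject can appear in both.

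SAP 10.2.2 also plans some AE tables "through the maintenance period for the MS (excluding patients randomized to ADA". By SAP 3.6, Maintenance Set summaries are shown as Q4W, Q4W/Q8W and Total, that is, by randomised arm. These versions are listed for the TEAE overview, TEAEs, serious TEAEs and TEAEs leading to discontinuation. The severity and relationship tables are listed only through Week 24 (Safety Set) and for the BKZ Set. SAP 10.2.3 defines the safety-topic tables per 100 subject years and names no analysis set for them.

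**The concern.** Every subject who receives bimekizumab starts on Q4W dosing, so every subject's early time on drug is counted as Q4W. The Q8W column holds only time after Week 16, in subjects who stayed long enough to be dosed in the Maintenance Treatment Period. A Q4W rate set beside a Q8W rate in these tables compares two regimens and two stretches of time on drug at once.

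If an event type is more frequent soon after starting bimekizumab, Q8W would show a lower exposure-adjusted rate even if the dosing interval made no difference. If it becomes more frequent with time, Q8W would show a higher one. The safety topics in 10.2.3 include fungal and opportunistic infections, neutropenia, inflammatory bowel disease, hypersensitivity and hepatic events. These are the tables a reader choosing between maintenance regimens is likely to consult, and the plan promises no other version of them.

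**Working it through.** The documents state no figure on this point, so there is none to reproduce.

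**Inputs.** Arm size: "There will be approximately 150 subjects per treatment arm" (SAP 2.3.4). Period lengths: "Double-blind, active-controlled Initial Treatment Period: 16 weeks" and "Maintenance Treatment Period: 40 weeks" (SAP 2.3.3). Adalimumab switchers take bimekizumab Q4W from Week 24 (SAP 2.3.2.3), so they have 56 − 24 = 32 weeks by Week 56. Simplifications: no dropout, and planned treatment time without safety follow-up. Assumption: k, the ratio of the event rate after the first 16 weeks on bimekizumab to the rate within them. The documents do not give k. It is taken as the same for both regimens, so there is no true regimen effect.

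**Step 1: planned person-weeks by column.**

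| Arm | Q4W column | of which first 16 weeks on drug | Q8W column |
|---|---|---|---|
| Q4W/Q4W | 150 × 56 = 8,400 | 150 × 16 = 2,400 | – |
| Q4W/Q8W | 150 × 16 = 2,400 | 2,400 | 150 × 40 = 6,000 |
| ADA/BKZ Q4W | 150 × 32 = 4,800 | 2,400 | – |
| Total | 15,600 | 7,200 (46.2%) | 6,000 (none early) |

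With linear dropout of 5% to 20% over 56 weeks, the early share of the Q4W column is 47% to 48%.

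**Step 2: exposure-adjusted event rate.** Set the early rate to 1 and the later rate to k. The Q8W rate is k. The Q4W rate is (7,200 + 8,400k)/15,600. The apparent Q8W/Q4W ratio is 15,600k/(7,200 + 8,400k).

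- k = 1 (constant): 15,600/15,600 = 1.00
- k = 0.75 (falls 25%): 11,700/13,500 = 0.87
- k = 0.5 (halves): 7,800/11,400 = 0.68
- k = 1.25 (rises 25%): 19,500/17,700 = 1.10

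The exposure-adjusted incidence rate behaves alike. At k = 0.5 its ratio is 0.68, 0.66 and 0.61 when the 40-week incidence at the later rate is 2%, 20% and 60%.

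**Step 3: crude percentages.** Mean planned time in column is 15,600/450 = 34.7 weeks for Q4W and 40 weeks for Q8W, which pulls the other way. Take a 40-week incidence of 20%, so the later weekly rate is λ = −ln(0.8)/40 = 0.00558, and k = 0.75, so each early week counts as 1/0.75 later weeks:

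- Q4W/Q4W arm: 16/0.75 + 40 = 61.33 weeks at λ, incidence 29.0%
- Q4W/Q8W arm to Week 16: 16/0.75 = 21.33 weeks, 11.2%
- Switchers: 21.33 + 16 = 37.33 weeks, 18.8%
- Q4W column: mean of the three, 19.7%. Q8W column: 20.0%

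At 2% incidence the columns are about equal. Q8W looks lower on crude percentages only if the early rate exceeds the later one by a factor of about 1.34, 1.38 or 1.52 (40-week incidence 2%, 20% or 60%), that is, if rates fall by more than about 25%, 28% or 34%.

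**Step 4: the like-for-like window.** On Weeks 16 to 56 by randomised arm, each regimen has 150 × 40 = 6,000 person-weeks from the same stretch of time on drug. With no regimen effect the ratio is 1.00 for any k.

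**Step 5: which tables have that window.**

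- TEAE overview, TEAEs, serious TEAEs and TEAEs leading to discontinuation: yes (10.2.2).
- Laboratory shift tables on the BKZ Set: shown by randomised arm (10.3), so the column rule does not affect them.
- Severity and relationship tables: no.
- Safety-topic tables: not stated.

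The Week 24 Safety Set tables cannot fill the gap. By SAP Table 7-1 both bimekizumab arms receive active drug at Week 16 and first differ at Week 20, which leaves about four weeks of divergence.

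**The case against.** The strongest reply is that the comparison that matters most is already planned. SAP 2.2.3.1 lists three secondary safety variables: exposure-adjusted TEAEs, SAEs and TEAEs leading to withdrawal. Each has a matching Maintenance Set table per 100 subject years, and 10.2.2 requires both exposure-adjusted measures there. This stands, and it confines the point to other tables.

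Second, the severity and relationship tables report crude incidence, so the 0.87 and 0.68 of Step 2 do not describe them. This also stands. Those columns are still not comparable, because they differ in time on drug and in length of follow-up, but the direction is not fixed.

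Third, the safety-topic gap is partly one of silence. The opening of SAP 10 names the Maintenance Set among the sets used for safety, so such versions are not ruled out. Serious infections and injection site reactions are read from tables that have a Maintenance Set version, and some components of other topics can be found there by HLT or PT. The 5%-threshold tables are a filter on the same listing. Topic totals may not be recoverable, however, and the plan does not commit to them.

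Fourth, the objectives name Q4W versus Q8W only for maintenance of efficacy, and AE risk differences are bimekizumab versus adalimumab. The BKZ Set columns are descriptive. That lowers the stakes, but rates printed side by side will be compared.

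**Conclusion.** The point holds for the BKZ Set AE summaries and is limited in reach. Early time on bimekizumab makes up 46% of planned Q4W person-time and none of Q8W, so exposure-adjusted rates mix regimen with time on drug. The distortion is a ratio of 0.87 or 0.68 under assumed falls of 25% or 50%, none if rates are constant, and reversed if they rise. The documents give no event rates over time, so neither size nor direction is known.

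A reader might infer that Q8W will look safer in all BKZ Set safety tables whenever rates fall, or that the secondary safety variables lack a fair comparison of the regimens. The documents support neither. Crude percentages can leave Q8W equal or higher after a modest fall, the laboratory shift tables are by randomised arm, and the secondary safety variables have Maintenance Set tables. What remains is an inexpensive improvement for the safety-topic, severity and relationship tables.

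**What to change.** State in SAP 10.2.2 and 10.2.3 that the safety-topic, severity and relationship tables are also produced on the Maintenance Set, by randomised arm from Week 16, without subjects randomised to adalimumab. Footnote the Q4W and Q8W columns of the BKZ Set AE tables as non-randomised, different in time on drug, and not to be compared with each other.

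The cost is a few more tables from programs that already exist, with no new data. Removing the regimen columns altogether is not needed and would be a trade-off: showing only the Total loses information by regimen received, and showing randomised sequences mixes Q4W and Q8W time within the Q4W/Q8W arm.

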3.7 Center pooling strategy

Centers will be pooled into regions for analysis purposes. Geographic regions will be categorized as North America, Western Europe, Central/Eastern Europe, and Asia/Australia. Below is a table of geographic regions with corresponding countries.

Table 3–1: Geographic regions

Region	Countries
North America	Canada, United States
Western Europe	Germany
Central/Eastern Europe	Czech Republic, Hungary, Poland, Russian Federation
Asia/Australia	Australia, Republic of Korea, Taiwan

The following center pooling algorithm will be used for each geographic region:

- If a center has 15 or more subjects, then no pooling will be done for that center.
- Centers with fewer than 15 subjects will be ordered from largest to smallest with pooling proceeding in the following manner:
 - Two or more centers will be combined until the cumulative subject total is at least 15.
 - Once a pooled center has at least 15 subjects, the process will continue in an iterative fashion for the subsequent centers in the ordered list, where a new pooled center begins each time at least 15 subjects has been reached in the previous pool.
 - If this iterative process reaches the end of the ordered list of centers where the final pooled center has fewer than 15 subjects, then the subjects from the centers in that pool will be combined with the pooled center formed in the previous iteration.

This procedure is only to be performed within a geographic region –there will be no pooling of centers across regions.

In the event that the percentage of randomized subjects is less than 10% in either of the Asia/Australia or Western Europe regions, then the two regions will be combined as a

geographic region stratum for efficacy modeling, so that there are no modeling convergence issues across efficacy variables.

3.8 Coding dictionaries

All medications other than study drug will be classified by WHO Anatomical Therapeutic Chemical (ATC) Classification, presenting Anatomical Main Group (ATC Level 1), Pharmacological Subgroup (ATC level 3), and preferred term, using version SEP/2015 of the World Health Organization Drug Dictionary (WHO-DD), according to UCB standard operating procedures.

All AEs will be classified by primary system organ class (SOC), high level term (HLT) and preferred term (PT) using version 19.0 of MedDRA® according to UCB standard operating procedures.

Previous and ongoing medical history will be classified by version 19.0 of MedDRA® SOC and PT.

3.9 Relative day

The relative day will be included in different listings and will be calculated as follows:

- If the start (stop) date occurred on or after the first dose, but prior to the double-blind drug stop date, relative day is calculated as start (stop) date minus first dose date + 1
- If the start (stop) date occurred after the last dose of double-blind drug, the relative day to the most recent dose is calculated as start (stop) date minus most recent dose date. The relative day in this situation should be preceded by a '+'
- If the start (stop) date occurred before the first dose, the relative day is calculated as start (stop) date minus first dose date. The relative day in this situation should be preceded by a '-'.

For AEs, relative days for start and stop dates will be calculated as the number of days since the first injection of the medication. For non-treatment emergent AEs, relative day of onset will be negative if the event started and stopped before the first dose. Relative day will only be computed for fully completed dates and will be missing for partial dates.

Relative day will be calculated from first dose of IMP for all treatment groups, and additionally from first dose of bimekizumab for the ADA/BKZ 320mg Q4W arm.

3.10 Changes to protocol-defined analyses

For the following endpoints, the definition of response has been clarified:

- Scalp IGA response (clear or almost clear with at least a 2-category improvement from Baseline) for subjects with scalp PSO at Baseline
- Palmoplantar Investigator's Global Assessment (pp-IGA) response (clear or almost clear with at least a 2-category improvement from Baseline) for subjects with palmoplantar PSO at Baseline

The following endpoints are not listed in the protocol, but have been added to the SAP in order to achieve consistency with other studies from the program:

- mNAPSI75/90/100 response (defined as a subject that achieves at least a 75%, 90% and 100% reduction from Baseline in the mNAPSI score)
- Percent of subjects with absolute PASI score ≤ 1 , ≤ 2 , ≤ 3 , and ≤ 5
- Percent of subjects with absolute BSA=0%, $\leq 1\%$, $\leq 3\%$, and $\leq 5\%$
- The sensitivity analysis for the primary endpoint using MI-MCMC/reference based methods detailed in the protocol has been removed from the analysis plan because it could generate bias due to the reference arm being the active comparator.

The following additional changes were made:

- The calculation of nominal p-values has been added for selected efficacy variables
- Modifications have been made to the text regarding the multiple imputation algorithm for clarity
- Change from Baseline in PHQ-9 score is listed an efficacy variable in the protocol. However, it is considered as a safety variable in this SAP.
- Selected TEAE tables were added to include calculation of risk differences.

Urinalysis summaries were removed from the plan.

4 STATISTICAL/ANALYTICAL ISSUES

4.1 Adjustments for covariates

The primary efficacy analyses and selected secondary analyses will be adjusted for the following covariates:

- Prior biologic exposure
- Region

4.2 Handling of dropouts or missing data

4.2.1 Handling of missing data for efficacy variables

Based on previous studies of biologics in subjects with moderate to severe chronic plaque psoriasis, it is expected that the number of subjects who discontinue prior to Week 16 will be low. For the small percentage of subjects for whom primary endpoint data are unavailable at Week 16, this lack of data is suggestive of an ineffective study treatment, thereby supporting the imputation of non-response. Achieving the clinical response and making it through 16 weeks of study treatment are both critical components of the primary outcome. Therefore, non-responder imputation (NRI) will be used as the method for handling missing data in the primary analysis for binary efficacy variables.

If a subject discontinued study treatment without terminating from the study and still continues with scheduled assessments, all efficacy data after last treatment date + 35 days will be treated as missing and subject to imputation as applicable.

